## 7. DATA MANAGEMENT PLAN

### 7.1. Physical Controls

All data capture and storage methods will be HIPAA compliant as per MHS policy. All data will be collected and saved under the canteam files database. All study documents will be stored in a secure, limited access location behind two locked doors. The investigators will take measures to ensure that these essential documents are not accidentally damaged or destroyed. All clinical study documents will be retained by the CRI until at least three years after study completion or according to local laws, whichever is longer.

### 7.2. Technical Controls

All information will be kept under lock and key or on MHS approved password-protected servers at all times.

### 7.3. Source Document Management

The investigator(s)/institution(s) will permit study-related monitoring, audits, IEC/IRB review, and regulatory inspection(s), providing direct access to data collected via the Methodist Health System share drive. Data collected during this study will be recorded on the appropriate data source via Word document, Access database, or Excel spreadsheet depending on treatment type.

### 7.4. Data Capture Methods

Data will be collected with the assistance paper pre- and post-test. This data will be collected and transferred over into an Excel spreadsheet. All data collected will be entered in the appropriate document type. All data collection methodologies will be maintained under strict surveillance and will be encrypted.

### 7.5. Data Use and Sharing

Study data will not be shared with anyone that is not delegated to the study.

The PI is committed to disseminate research results in a timely fashion. Sharing of results generated by the data analysis during the course of the project will be through presentation at national scientific meetings and/or publication in open access journals. All information obtained will be source de-identified and presented on a large scale and not traceable to any one particular individual.

## **8. RECORD RETENTION/ARCHIVING**

The investigator will maintain the original formats of all essential study documents and source documentation at the investigative site in compliance with ICH/GCP guidelines. All study-related documents will be retained by the CRI until at least three years after study completion or according to local laws, whichever is longer. The investigator will take measures to ensure that these essential documents are not accidentally damaged or destroyed. If, for any reason, the investigator withdraws responsibility for maintaining these essential documents, custody of the documents will be transferred to an individual who will assume responsibility; the CRI and IRB will receive written notification of this custodial change. Records will also be accessible to MHS staff upon request unless constituting a violation of patient confidentiality.

## **9. PUBLICATION PLAN**

All information will be blinded in compliance with GCP. The investigator will make all possible efforts to ensure compliance with all policies regarding sharing of PHI or

research information. Only de-identified PHI will be shared in relevant research  
mediums.

**10. BUDGET**

Services	Cost	Total Cost (with 30% indirect cost)
IRB Fees		
Initial Study Review Fee (Includes 1 informed consent)	\$1,265	\$1,644.50
Continuing Review for Main Study File	\$880	\$1,144.00
Study Close Out - Study Level	\$275	\$357.50
Review of Subject Materials: Per Document (Ads, retention, protocol clarification, etc.)	\$240	\$312.00
Protocol Amendment Per Site (no Revised Informed Consent)	\$345	\$448.50
Protocol Amendment Per Site (with Revised Informed Consent)	\$420	\$546.00
Acknowledgement of Submissions (Safety Reports, etc.)	\$50	\$65.00
Administrative Fees	\$5,000	\$6,500.00
Data Collection (per hour)	\$50	\$65.00
Data Analysis (X hours, \$75/h)	\$0	\$0
Education and Training	\$0	\$0
Subject Stipend(s)	\$0	\$0
Study Coordination (per hour)	\$20	\$26.00
Archiving	\$600	\$780.00
Total	\$9,145.00	\$11,888.50

## Appendix B: Data Collection Tool

## Excel Spreadsheet: Pre-Test

## Excel spreadsheet: Post-Test

## Appendix C

### Pre-Test

1. Do you or have you ever smoked tobacco cigarettes?
  - a. Yes, I currently smoke
  - b. Yes, I smoked in the past
  - c. No, I never smoked
2. Do you or have you ever used a vape pen, e-cigarette, or other vaping products?
  - a. Yes, I currently use these products
  - b. Yes, I have tried these products in the past
  - c. No, I never used these products
3. How often do you vape?
  - a. Everyday
  - b. 3 to 5 times a week
  - c. Once a week
  - d. Few times a month
  - e. Never
4. How long have you been vaping and/or using tobacco products?
  - a. Less than 3 months ago
  - b. 6 months ago
  - c. About 1-2 years ago
  - d. More than 2 years ago
  - e. I never have
5. Using vaping products will help you stop smoking cigarettes?
  - a. True
  - b. False
6. Using vaping products may cause harm to my health?
  - a. True
  - b. False
7. By using vaping products, I am more likely to smoke cigarettes in the future.
  - a. True
  - b. False
8. There are currently \_\_\_\_ million students that use vaping products
  - a. 1 million
  - b. 3.5 million
  - c. 8 million
  - d. 5.3 million
9. Students who vape are \_\_\_\_ more likely to begin smoking cigarettes
  - a. twice

b. four times  
c. five times  
d. ten times

10. There are at least \_\_\_\_ confirmed vape related deaths as of January 21st, 2020  
a. 15  
b. 35  
c. 60  
d. 2

11. People vape because \_\_\_\_  
a. It helps them to relax  
b. Their friends or family vape  
c. They like the taste of it  
d. They think it is safer than tobacco cigarettes  
e. All the above

12. I feel pressured to vape.  
a. Yes  
b. No  
c. Sometimes

13. Effects that vaping has on my body are \_\_\_\_  
a. Decreased brain development  
b. Problems with breathing  
c. Increase heart rate  
d. Higher chance of developing cancer  
e. All the above

14. How likely are you to use vaping products?  
a. Not at all  
b. Not sure  
c. Very likely  
d. I already vape

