Many vaping companies present their products as nicotine free and as being a safe and non-addictive way of smoking. From commercials to online ads, consumers are being told that this product is free from the smell of cigarettes, reusable, much cheaper, and even healthier than traditional cigarettes. This information can be very deceiving and persuasive to the young mind.

This program titled, “To Vape or Not to Vape”, will provide education to adolescents and young adults about the potential risk of vaping in an effort to assist with lowering the usage rates within the population. Content will include information about current statistics, potential short-term and long-term side-effects, and healthy alternatives for dealing with stress and peer-pressure. We anticipate that this program will increase this population’s knowledge about the risks of vaping products, and deter them from future use of the products. Effectiveness of this program will be measured by pre and post-tests.

**1.2.** Aim(s)/Objective(s)

The overall goal of this study is to increase knowledge of vaping and its associated risks. This study will find the patterns of vaping, and how it all started among adolescents. We want to know if students are aware of the serious and long term effects of vaping.

The objectives are:

1. To provide at least 100 middle school and high school students with anti-vaping education.
2. To provide at least 40 college students with anti-vaping education.
3. To improve the overall knowledge of vaping statistics and side effects as measured by a pre and post-test. The pre-test will be the baseline measurement. The post-test will be the measure of effectiveness. Out of the 10 questions on the post-test, the goal is to have the students answer at least 8 out of the 10 questions correctly.
4. To decrease the percentage of students who say that they are likely to vape in the future.

The program will be going to middle school, high school, and college campuses in the Dallas-Fort Worth (DFW) area to speak with students about vaping. The program will be implemented by community outreach, as the students will be presented with information about vaping and the resources necessary to prevent or stop vaping. This program will present the students with a 35-minute curriculum that is listed below. The purpose of this study is to relay

and publish data that will support education about vaping and the many health risks associated with vaping products.

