**2. OBJECTIVES AND STUDY OUTCOME MEASURES**

**2.1.** Study Objectives

**2.1.1.** Primary Objective(s)

The primary objective for this program is to obtain an understanding and gather information on the percentage of vape users in teens and young adults. This study will include at least 100 individuals, as this will allow us to determine why vaping is so prominent, what causes individuals to be attracted towards this habit, and determine why there is an increasing rate of vaping.

**2.1.2.** Secondary Objective(s)

The secondary objective for this program is to prevent those who do not vape to not begin to partake in this habit and to reduce the percentage pf the target population who are currently vaping, by increasing their knowledge on the dangers of vaping by 10%.

**2.2.** Study Outcome Measures

**2.2.1.** Primary Outcome(s)

We will obtain the percentage of vape users and their reasons for vaping from information gathered from pre-test (Appendix C). Within 6 months, we hope to see a decline in the usage of vapes in the DFW area.

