### 2.2.2. Secondary Outcome(s)

Changes in the degree of understanding will be assessed from the results of the pre- and post-test (Appendix C). In addition, we hope to find the answers to the following questions:

- Is vaping within the student's environment?
- Are the students being socially peer pressured into smoking, and if so how often?
- Are most students forming addictive behaviors towards vaping?
- What are the triggers that cause a student to vape?
- What is their reasoning on why they vape or participate in any smoking products?
- Do members of their close group of friends' vape?
- Are students aware of the serious and long-term side effects of vaping?

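### Pre-test items 3 and 4 leave gaps in vaping frequency and duration, and item 4 merges vaping with tobacco, so some usage-pattern answers will be misclassified or lost

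*Combined protocol and SAP*

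**What the plan says.** Section 1.2 states the aim: "This study will find the patterns of vaping, and how it all started among adolescents". Section 2.2.2 adds a list of questions, one of which is "Are most students forming addictive behaviors towards vaping".

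The instrument is the pre-test in Appendix C.

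- **Item 3**, "How often do you vape", offers five answers: daily, "3 to 5 times a week", once weekly, "Few times a month", and never.
- **Item 4**, "How long have you been vaping and/or using tobacco products", also offers five: "Less than 3 months ago", six months, roughly one to two years, over two years, and never.

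Neither item has an open or 'other' answer. Items 1 and 2 ask separately about cigarette smoking and vaping, each as current, past or never.

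The post-test has ten items and repeats none of pre-test items 1 to 4. Section 3 describes an anonymous study with a single session of about 35 minutes. Section 5.2 summarises categorical variables as counts and proportions. Neither Section 5.2 nor Section 7 gives a rule for coding an answer that fits no option.

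**The concern.** A categorical item that is tabulated as it stands needs options that cover every possible answer, and it should ask one thing. Item 3 fails the first requirement and item 4 fails both. A student whose true answer has no box must choose a neighbouring one or leave the item blank. The form does not say which, so two students with the same history may be recorded differently.

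These are the only frequency and duration data in the study, and Section 1.2 intends publication. Whatever distribution the boxes produce becomes the reported pattern of use.

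The merged wording falls on a group the sponsor expects to meet: Section 1.1 says that vape users are four times more likely to use tobacco and smoke cigarettes. Once the anonymous forms are collected, no student can be asked what was meant.

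**Working it through.** The plan gives no figure on this point to reproduce. The sample size in Section 5.1 concerns the paired comparison and has no bearing here. The check is to list which true answers have a box.

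**Item 3, times per week (daily counted as 7)**

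- 1: once weekly
- 2: no option
- 3, 4, 5: second option
- 6: no option
- 7: daily

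Two of the seven weekly counts have no option. At the low end, once a month or less falls between a few times monthly and never, and has none either.

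**Item 4, whole months, read literally**

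- 0, 1, 2: first option
- 3, 4, 5: no option
- 6: second option
- 7, 8, 9, 10, 11: no option
- 12 to 24: third option
- above 24: fourth option

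In the first year, 3 + 5 = 8 of the 12 whole months have no option. If students round, these months move to a neighbouring box, but nothing tells them to round or in which direction.

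**Item 4, stem against options.** The stem asks how long use has lasted, while the options are phrased as time before now. A student who vaped for two months and stopped three years ago could tick the shortest category (duration) or the longest (time since use). Both readings are defensible.

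**Item 4, two products in one answer.** Crossing items 1 and 2 shows what can be recovered:

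| Item 1 (cigarettes) | Item 2 (vaping) | What item 4 can tell us |
|---|---|---|
| Never | Current or past | Vaping, provided no other tobacco was used (item 1 covers cigarettes only) |
| Current or past | Never | Tobacco; set aside for vaping |
| Never | Never | Nothing needed on vaping |
| Current or past | Current or past | Not separable, except that the under-three-months answer, read as time since starting, bounds both products |

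For the other users of both products, if the longer use is what they report, item 4 gives only an upper bound on vaping duration. A smoker of three years who began vaping last month is recorded in the over-two-years category.

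**Scale, as an illustration only.** Section 5.1 plans 100 subjects. Section 1.1 gives 12% and 28% for high school vaping in 2016 and 2019.

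- Students supplying pattern data: 100 × 0.12 = 12 to 100 × 0.28 = 28.
- Assume that 10% to 30% of them fall in a gap. This range is an assumption; no document gives it.
- Affected: 12 × 0.10 = 1.2 to 28 × 0.30 = 8.4, or about 1 to 8 students.

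Past users also answer item 4. Using the roughly 40% in Section 1.1 who have tried vaping, 100 × 0.40 = 40 students, and the same assumption gives 40 × 0.10 = 4 to 40 × 0.30 = 12.

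**The case against.** The strongest reply is that little of importance depends on these two items. The primary outcome in Section 2.2.1 is the percentage of vape users and their reasons for vaping. The percentage comes from item 2, which keeps vaping separate from cigarettes and has no such gaps. Items 3 and 4 do not supply the reasons either. Neither item is on the post-test, so neither can enter the paired t, Wilcoxon or McNemar tests of Section 5.2. All of this stands. A reader might infer that the primary result or the pre/post analysis is compromised; the documents do not support that.

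The second reply is that the damage is partial. Item 3 is ordinal, so a student who vapes two or six times a week will probably pick a neighbouring category, and the gradient from daily to never survives. An infrequent current user who ticks never on item 3 can be spotted from item 2. Item 4 can be read for vapers who never smoked, subject to other tobacco use. This also stands, so it would be wrong to call the data beyond repair or to say that every user of both products gives a meaningless answer.

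The reply does not close the gaps, resolve the ambiguity for past users, or separate the two products for most of those who use both. Section 1.2 states the patterns of vaping as something the study will find, so the items cannot be set aside as incidental.

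**Conclusion.** The point holds as a limited measurement defect. Some frequency and duration answers will be misclassified or left blank, and for most users of both products the duration of vaping will stay unresolved. What suffers is the descriptive aim in Section 1.2 on patterns of vaping and how it started.

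The size is not known. Two of seven weekly counts and eight of the first twelve months describe how much of the answer scale is uncovered, on a literal reading that gives no weight to rounding. They are not the share of students affected, and the documents give neither a frequency distribution nor a dual-use prevalence. The figures of about 1 to 8 students for current vapers, or 4 to 12 if all who have tried vaping are counted, rest on the assumed 10% to 30% and on applying the Section 1.1 percentages to this sample.

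A reader might also infer that the gaps are what prevents an answer on addictive behavior in Section 2.2.2. The pre-test has no question on craving, loss of control or attempts to quit, so filling the gaps would not supply that answer.

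This is a cheap improvement, worth making before the form is used.

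**What to change.** Before printing, change the two items.

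- **Item 3:** every day; 3-6 days a week; 1-2 days a week; 1-3 days a month; less than once a month; never. This counts days throughout and keeps a monthly category.
- **Item 4:** replace it with two items, *How long ago did you first use vaping products?* and the same question for tobacco products. Each has: less than 3 months; 3 to less than 6 months; 6 to less than 12 months; 1-2 years; more than 2 years; never. Asking about first use removes the ambiguity for past users and matches the aim of learning how vaping started. It does not record how long a past user continued.

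Add the matching column to the Appendix B spreadsheet, and state in Section 5.2 how blank or double answers will be coded.

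The cost is one extra question. The pre-test goes from 14 to 15 items in its 5 minutes, or from 300/14 = 21.4 to 300/15 = 20 seconds per item. No sample size, test or schedule changes. If the form already has IRB approval, Section 6.2 requires the amendment to be approved before use; Section 10 lists $345 before indirect costs for an amendment without a revised consent form.

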## Appendix C

### Post-Test

1. Using vaping products will help you stop smoking cigarettes?
  - a. True
  - b. False
2. Using vaping products may cause harm to my health?
  - a. True
  - b. False
3. By using vaping products, I am more likely to smoke cigarettes in the future.
  - a. True
  - b. False
4. There are currently \_\_\_\_ million students that use vaping products
  - a. 1 million
  - b. 3.5 million
  - c. 8 million
  - d. 5.3 million
5. Students who vape are \_\_\_\_ more likely to begin smoking cigarettes
  - a. twice
  - b. four times
  - c. five times
  - d. ten times
6. There are at least \_\_\_\_ confirmed vape related deaths as of January 21st, 2020
  - a. 15
  - b. 35
  - c. 60
  - d. 2
7. People vape because \_\_\_\_
  - a. It helps them to relax
  - b. Their friends or family vape
  - c. They like the taste of it
  - d. They think it is safer than tobacco cigarettes
  - d. All the above
8. I feel pressured to vape.
  - a. Yes
  - b. No
  - c. Sometimes

9. Effects that vaping has on my body are \_\_\_\_\_

- a. Decreased brain development
- b. Problems with breathing
- c. Increase heart rate
- d. Higher chance of developing cancer
- e. All the above

10. How likely are you to use vaping products?

- a. Not at all
- b. Not sure
- c. Very likely
- d. I already vape

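### Every option of the bodily-effects item (pre-test 13, post-test 9) asserts a harm, so it overstates awareness of side effects; add 'None of these' and 'Don't know'

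*Combined protocol and SAP*

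**What the plan says.** Section 2.2.2 lists among the questions the study hopes to answer: "Are students aware of the serious and long-term side effects of vaping". Section 1.2 gives the same aim: "We want to know if students are aware of the serious and long term effects of vaping".

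In Appendix C, pre-test item 13 and post-test item 9 share the stem "Effects that vaping has on my body are". The options are four harms, one of them "Higher chance of developing cancer", and 'All the above'. There is no 'None of these' and no 'Don't know'.

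Pre-test item 6 (post-test item 2) is True/False: "Using vaping products may cause harm to my health". It concerns harm in general.

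The only option on either form that admits uncertainty is 'Not sure', under the intention item "How likely are you to use vaping products". The documents give no answer key, link no item to the awareness question, and do not say how a blank answer is handled.

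**The concern.** The effects item is the only one that names what vaping may do to the body, so it is the natural source for an answer to the 2.2.2 question. Its options presuppose that effects exist and that the student knows at least one. A student with no idea, or one who thinks vaping is harmless, must either assert a harm or skip the item.

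What is at stake is a descriptive result: the percentage aware before the session, and how far it moves afterwards. A percentage from this item will be too high by an amount that depends on guessing and on a scoring rule nobody has written down. Enrolling more students does not remove that bias.

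**Working it through.** The plan gives no expected awareness percentage, so there is no figure of its own to reproduce. The sample size in Section 5.1 (35, or 44 after 20% attrition) does not enter this point.

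**Inputs from Appendix C.** The effects item has five options, all harms. The general-harm item has two options.

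**Assumptions.** A share *u* of students is unaware, taken as 10%, 30% or 50%. Unaware students choose evenly among the printed options. Aware students choose 'All the above' on the effects item and 'True' on the general-harm item. Nobody leaves a blank.

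**Formula.** If an unaware student is counted as aware with probability *g*, then

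observed awareness = (1 − u) + u × g.

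- Effects item, only 'All the above' counts: g = 1/5 = 0.20.
- Effects item, any option counts: g = 1, because every option is a harm.
- General-harm item, 'True' counts: g = 1/2 = 0.50.

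| Unaware (u) | True awareness | Effects item, 'All the above' only | Effects item, any option | General-harm item |
|---|---|---|---|---|
| 10% | 90% | 0.90 + 0.10 × 0.20 = 92% | 100% | 0.90 + 0.10 × 0.50 = 95% |
| 30% | 70% | 0.70 + 0.30 × 0.20 = 76% | 100% | 0.70 + 0.30 × 0.50 = 85% |
| 50% | 50% | 0.50 + 0.50 × 0.20 = 60% | 100% | 0.50 + 0.50 × 0.50 = 75% |

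The overstatement on the effects item is therefore 2, 6 or 10 points under the strict rule and 10, 30 or 50 points under the lenient one. Under the lenient rule, no change from pre-test to post-test could appear on this item.

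**Sensitivity to the assumptions.**
- Blanks counted as not aware reduce the overstatement.
- Blanks dropped as missing remove unaware students from the denominator. If all of them skipped the item, it would show 100%.
- Students drawn towards 'All the above' because it looks like the intended answer raise g above 0.20.
- Under the strict rule, a student who knows of one listed harm and ticks only that one is scored as not aware, which works in the opposite direction.

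**The case against.** The strongest reply is that non-awareness can already be recorded. A student who thinks vaping is harmless can answer 'False' on the general-harm item. If only 'All the above' is correct on the effects item, 80% of even guessers are scored as not aware.

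This disposes of some stronger readings. A reader might infer that the 2.2.2 question cannot come out 'no', or that neither form can register unawareness. The documents do not support either: 'False' is available, and the effects item can be answered wrongly under a strict key. Nor are unaware students recorded as aware as a rule, since that depends on the key.

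The reply does not rescue the effects item. The general-harm item asks whether harm is possible, not what the serious or long-term effects are. The strict key is a reasonable guess, but it is not written down.

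A second reply is that 'Don't know' options have their own bias. After a persuasive session students may be readier to commit to an answer without having learned more, and a high 'Don't know' rate leaves out those who are confidently wrong. That stands. It is why 'Don't know' should be reported separately and not used alone as the awareness figure.

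A reader might also extend the criticism to all eight knowledge items (pre-test 5–11 and 13) and ask for 'Don't know' with an instruction not to guess throughout. None has that option, but pre-test items 8–11 ask about user numbers, the relative likelihood of smoking, a death count and reasons for vaping. Guessing there says little about side-effect awareness. The wider change is optional.

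**Conclusion.** The point holds for one item. The effects item cannot record a student who knows of no effect or believes there is none, so awareness taken from it is overstated. With 30% unaware and guessing evenly, it shows 76% in place of 70% if only 'All the above' counts, and 100% if any option counts. The direction follows from the printed options. The size rests on the assumed unaware share, even guessing, no blanks, aware students choosing 'All the above', and a key the documents do not give.

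One might go on to infer that guessing would make the program miss its 10% knowledge gain in Section 2.1.2. The documents do not support that. They do not say whether 10% is relative or in points, and Section 2.2.2 assesses change from the test results, which are observed scores. Nor is the paired analysis shown to fail: the item is the same on both forms, and 100 students are planned against 35 required. This is a cheap improvement to the questionnaire, not a flaw in the main analysis.

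**What to change.** Before the forms are printed:

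1. Add 'None of these' and 'Don't know' to pre-test item 13 and post-test item 9, and score both as not aware.
2. State in Section 5.2 which answers to this item count as aware and how a blank is counted.
3. Answer the 2.2.2 awareness question by reporting, at pre-test and post-test, the percentages choosing 'None of these', 'Don't know' and a wrong answer on the effects item, together with the percentage answering 'False' on the general-harm item (pre-test 6, post-test 2).

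The cost is two printed lines on each form and a few sentences in the plan, with no extra students and negligible time. The measured baseline may look lower. Some students may tick 'Don't know' from disinterest, or tick it less after the session because they are readier to answer, so keep the two new options separate in the report. Some guessing will remain.
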